6.1.1.1. Sensitivity/Supplementary Analysis

As a sensitivity analysis, the prevalence will be estimated using the diagnosis criteria described in the primary endpoint, but will include all participants with Scintigraphy Grade 1 diagnosed with ATTR-CM in the study (regardless of the cardiac biopsy). Specifically, participants with Scintigraphy Grade 1 that were diagnosed with ATTR-CM using a criteria other than cardiac biopsy will be included in the estimate of prevalence in this sensitivity analysis. Scintigraphy Grade 1 participants that are lost to follow-up prior to a diagnosis of ATTR-CM will be assumed as not diagnosed with ATTR-CM. The proportion of Scintigraphy Grade 1 participants that are diagnosed with ATTR-CM will be estimated.

6.2. Secondary Endpoint(s)

The Secondary endpoints listed below will be compared between HFpEF participants with and without ATTR-CM as defined in [Section 6.1.1.1](#).

- The prevalence of ATTR-CM in HFpEF participants will be evaluated for subgroups including regions (North America, Europe, and Asia), age categories (60-64, 65-69, 70-74, 75-79, 80-85, >85), and gender (male, female). Exact 95% confidence intervals for the prevalence in subgroups will be calculated using the method of Clopper and Pearson.¹ Prevalence estimates along with 95% CIs will be generated for subgroups with at least 50 participants. For subgroups that enroll fewer than 50 participants, prevalence will not be estimated. These secondary analyses will be generated using the “Evaluable Analysis Set”.
- Participants diagnosed with ATTR-CM will be evaluated for TTR genotype, ie, wild-type or hereditary form. The proportions of these two genotypes will be evaluated as a secondary endpoint using descriptive statistics only (ie, number and percentage).
- NYHA classification proportions will be compared between HFpEF participants diagnosed with ATTR-CM and those that are not diagnosed with ATTR-CM using the Chi-square test. Fisher’s exact test will be used instead if any one of the cells has ≤ 5 participants. Proportion of NYHA classifications will also be descriptively summarized (frequency tables) by scintigraphy grade for participants who are diagnosed with ATTR-CM. Participants with non-evaluable scintigraphy grade will be summarized in a separate group.
- NT-proBNP will be compared between HFpEF participants diagnosed with ATTR-CM and those that are not diagnosed with ATTR-CM using a Wilcoxon rank sum test.

- NT-proBNP (mean, standard deviation, median, IQR, minimum and maximum) will be descriptively analyzed by scintigraphy grade and NYHA classification for participants who are diagnosed with ATTR-CM. Participants with non-evaluable scintigraphy grade will be summarized in a separate group.

CCI

CCI

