8.2.11. NYHA Classification

The extent of participants' heart failure will be evaluated at Visit 1 using the New York Heart Association (NYHA) classification.

Class I: Participants with cardiac disease but without resulting limitations of physical activity. Ordinary physical activity does not cause undue fatigue, palpitation, dyspnea, or anginal pain.

[figure not shown]
Class II: Participants with cardiac disease resulting in slight limitation of physical activity. They are comfortable at rest. Ordinary physical activity results in fatigue, palpitation, dyspnea, or angina pain.

Class III: Participants with cardiac disease resulting in marked limitation of physical activity. They are comfortable at rest. Less than ordinary physical activity causes fatigue, palpitation, dyspnea, or anginal pain.

Class IV: Participants with cardiac disease resulting in inability to carry on any physical activity without discomfort. Symptoms of cardiac insufficiency or of the anginal syndrome may be present even at rest. If any physical activity is undertaken, discomfort is increased.

CCI

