9. STATISTICAL CONSIDERATIONS

Detailed methodology for summary and statistical analyses of the data collected in this study will be documented and will be maintained by the sponsor.

The primary completion date (PCD) for the global prevalence estimate will be the date when all enrolled participants have either been diagnosed with ATTR-CM (scintigraphy grades 2 or 3), have scintigraphy grade 1 or found to be negative for ATTR-CM (scintigraphy grade 0) and have completed Follow-up Visit 1. Results will be reported after PCD and at the end of study (LPLV for participants with scintigraphy grade 1, 2 or 3).

The empirical estimate for the prevalence of ATTR-CM in HFpEF participants is approximately 10%. The study will enroll approximately 2000 HFpEF participants within whom it is expected to detect 200 ATTR-CM participants. Enrollment will be stopped if 200 ATTR-CM participants are identified before 2000 HFpEF are enrolled. No formal sample size calculation was performed. A sample size of 2000 HFpEF participants would be sufficient to inform treatment guidelines and yield an estimate for the global prevalence of ATTR-CM in HFpEF participants with a precision of $\pm 2.5\%$.

The primary endpoint is an estimate of the global prevalence of ATTR-CM in HFpEF participants. Diagnosis of ATTR-CM is defined as:

- Cardiac Scintigraphy Grade 1, with confirmation of ATTR by cardiac biopsy; or
- Cardiac Scintigraphy Grade 2 or above.

This global prevalence estimate will be obtained by dividing the number of participants who are diagnosed with ATTR-CM in the study by the total number of HFpEF participants evaluated. A 95% confidence interval on the estimate will also be calculated.

As secondary analysis, prevalence will be estimated for:

- Regions and countries.
- Age categories (60-64, 65-69, 70-74, 75-79, 80-85, >85).
- Gender (male, female).

Prevalence estimates along with 95% CI will be generated for regions and countries with at least 50 participants. For regions and countries that enroll fewer than 50 participants, prevalence will not be estimated. Regions will be defined in the statistical analysis plan. The proportion of HFpEF participants who were diagnosed with wild-type and variant ATTR-CM will be descriptively summarized.

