As a general rule, the secondary endpoints other than the prevalence estimates and all CCI reported as numerical values will be analyzed descriptively using mean, standard deviation, median, minimum and maximum. Endpoints that are categorical will be summarized using frequency tables.

Analysis by Scintigraphy:

Participants who are diagnosed with ATTR-CM will be analyzed by scintigraphy grades (Grade 1, 2, or 3) using the 6-MWT, NT-proBNP, medical history, demographics (including age, TTR Genotype, gender and race), NYHA classification (Class I, II, III, or IV), and all CCI

Analysis by Disease Status:

Participants who are diagnosed with ATTR-CM will be analyzed by NYHA Classification (Class I, II, III, or IV) using the 6-MWT, NT-proBNP, medical history, demographics (including age, TTR Genotype, gender, and race) CCI

Participants who are diagnosed with ATTR-CM will also be analyzed by 6-MWT quartile groups using NYHA baseline classification (Class I, II, III, or IV), NT-proBNP, medical history, demographics (including age, TTR Genotype, gender, and race) CCI

Analysis Comparing ATTR-CM participants with HFpEF patients without ATTR-CM:

HFpEF participants diagnosed with ATTR-CM will be compared with HFpEF participants not diagnosed with ATTR-CM descriptively using medical history, demographics (including age, TTR Genotype, gender, and race) CCI

Medical history data will be used to generate descriptive statistics for time from symptom onset to HFpEF diagnosis and time from symptom onset to ATTR-CM diagnosis.

Endpoints measuring proportion of participants (NYHA Classification and symptoms of interest from medical history) will be compared between HFpEF participants diagnosed with ATTR-CM and those that are not diagnosed with ATTR-CM. The Chi-square test will be used to compare the proportions between these 2 groups of HFpEF participants. Fisher's exact test will be used instead of the chi-square test if any one of the cells has ≤ 5 participants. Secondary CCI endpoints that are normally distributed will be compared between 2 groups of HFpEF participants using a t-test. Endpoints that are not normally distributed will be compared using the Wilcoxon rank sum test.

Safety Analysis:

Adverse events (AEs) and research related injuries (RRI) collected at Visit 1 or during Follow-up visits, will be summarized overall and separately for HFpEF participants diagnosed with ATTR-CM and HFpEF participants not diagnosed with ATTR-CM.

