3.2. Secondary Endpoint(s)

The secondary endpoints are listed below will consider a participant as diagnosed with ATTR-CM based on the definition in [Section 6.1.1.1](#).

- Estimate of prevalence of ATTR-CM in participants with HFpEF within the following subgroups, where prevalence within each subgroup is defined as the number of participants meeting the diagnosis criteria in [Section 6.1.1.1](#) divided by the number of evaluable participants in the study in the given subgroup category:
 - Regions (North America, Europe, Asia);
 - Age categories (60-64, 65-69, 70-74, 75-79, 80-85, >85);
 - Gender (male, female).
- Participants diagnosed with ATTR-CM will be evaluated for TTR genotype, ie, wild-type or hereditary form. The proportions of these two genotypes will be evaluated as a secondary endpoint
- Baseline characteristics of HFpEF participants with and without ATTR-CM:
 - NYHA classification: Participants will be evaluated using the New York Heart Association classification at baseline visit (day 1). Detailed description of each class (Class I, Class II, Class III, Class IV) is available in Section 8.2.12 of the protocol.
 - NT-proBNP: A biomarker that will be assessed during visit 1.

CCI

CCI

CCI

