5.2.3. Analyses for Categorical Endpoints

Secondary endpoints that are categorical will be summarized descriptively using frequency tables. The Chi-square test will be used to compare the proportions between HFpEF participants diagnosed with ATTR-CM as defined in [Section 6.1.1.1](#) and those that are not diagnosed with ATTR-CM, where applicable. Fishers exact test will be used instead of the chi-square test if any one of the cells has ≤ 5 participants.

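### NYHA class is an ordered scale, but the plan compares it only with tests that ignore the order and give no estimate of the shift; an ordinal comparison should be added.

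*SAP*

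**What the plan says.** NYHA classification is a secondary endpoint in both documents, listed under baseline characteristics of participants with and without ATTR-CM. For the comparison of the two groups, SAP 6.2 says: "NYHA classification proportions will be compared between HFpEF participants diagnosed with ATTR-CM and those that are not diagnosed with ATTR-CM using the Chi-square test". For sparse tables the same section switches to Fisher's test; a single cell of five or fewer is enough to trigger it.

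SAP 5.2.3 gives the same general rule for categorical endpoints: "Fishers exact test will be used instead of the chi-square test" when a cell is small. Protocol 9 puts NYHA and symptoms from the medical history together and says: "The Chi-square test will be used to compare the proportions between these 2 groups of HFpEF participants".

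The classes are graded in Protocol 8.2.11 (SAP 3.2 points to 8.2.12). They run from no limitation, through slight limitation, to "Class III: Participants with cardiac disease resulting in marked limitation of physical activity", and then to inability to carry on any activity without discomfort.

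The readable text plans no rank test, trend test or ordinal model for NYHA, and no odds ratio or interval. SAP 5.2.3 does plan frequency tables, and Appendix 1 of the SAP marks NYHA for comparison between participants with and without ATTR-CM.

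**The concern.** The natural question for a severity scale is whether one group sits higher on it. A 2 x 4 chi-square test, or Fisher's test on the same table, does not ask that. Permuting the four class labels leaves the p-value unchanged, and the test spreads its 3 degrees of freedom over every kind of difference between the two sets of proportions.

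Two things follow. If participants with ATTR-CM are moderately worse in NYHA class, the planned test is less likely to show it than a test that uses the order. And the plan yields a p-value beside a table of percentages, with no single figure for the size of the shift and its uncertainty.

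**Working it through.** **Inputs from the documents.** Protocol 9: "The study will enroll approximately 2000 HFpEF participants within whom it is expected to detect 200 ATTR-CM participants". The stated prevalence of about 10% reproduces this: 0.10 x 2000 = 200, which leaves 2000 − 200 = 1800 without ATTR-CM. There are four NYHA classes, so the chi-square has (2 − 1) x (4 − 1) = 3 df.

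**Inputs assumed.** The documents give no NYHA distribution, effect size, power or significance level for this comparison. I take a two-sided 5% level, a range of class distributions in the group without ATTR-CM, and a proportional-odds shift:

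odds(class ≥ k, ATTR-CM) = OR x odds(class ≥ k, no ATTR-CM), for k = II, III, IV.

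Example: 12/50/35/3% in classes I to IV and OR 1.5.
- Class ≥ II: 0.88/0.12 = 7.33; x 1.5 = 11.0; probability 0.917.
- Class ≥ III: 0.38/0.62 = 0.613; x 1.5 = 0.919; probability 0.479.
- Class IV: 0.03/0.97 = 0.0309; x 1.5 = 0.0464; probability 0.044.

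By subtraction the ATTR-CM group is 8.3/43.8/43.5/4.4%.

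**Tests compared.**
- Chi-square: X² = Σ(O − E)²/E on 3 df.
- Wilcoxon with mid-ranks: z = [W − n₁(N + 1)/2]/√V, where V = (n₁n₀/12)[(N + 1) − Σ(t³ − t)/(N(N − 1))] and t is the total in each class.

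**Simulated power,** 20,000 tables per row, 200 v 1800, distribution 12/50/35/3%:

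| OR | Chi-square | Wilcoxon | Gap (points) |
|---|---|---|---|
| 1.3 | 32% | 46% | 14 |
| 1.4 | 50% | 66% | 16 |
| 1.5 | 68% | 82% | 14 |
| 1.75 | 93% | 98% | 5 |
| 2.0 | 99.2% | 99.8% | under 1 |

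Type I error is about 5% for both tests. A second distribution (20/55/23/2%) gives 32% v 45%, 50% v 65% and 67% v 81% at OR 1.3, 1.4 and 1.5. Four further distributions (10/60/28/2, 5/65/28/2, 15/50/30/5 and 25/25/25/25%) give losses of about 10 to 17 points over OR 1.25 to 1.5, 3 to 6 points at OR 1.75, and about 1 point or less at OR 2. In those four, a linear trend test stays within about 1.5 points of Wilcoxon. With 100 v 1900 at OR 1.5, the powers are 37-43% and 51-60%.

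**Analytic check.** For 80% power at 5%, the required noncentrality is 7.85 on 1 df and 10.90 on 3 df. The ratio is 10.90/7.85 = 1.39, so about 39% more participants would be needed for equal power. At noncentrality 7.85 the 3-df test has 64% power.

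**The other direction.** Compare 10/60/28/2% without ATTR-CM and 15/50/32/3% with it, so that ATTR-CM is over-represented at both ends of the scale. Chi-square has 73% power and Wilcoxon about 9%.

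**Fisher fallback.** P(5 or fewer of 200 in Class IV), binomial:

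| Class IV in the group without ATTR-CM | No shift | OR 1.3 | OR 1.5 |
|---|---|---|---|
| 2% | 0.79 | 0.59 | 0.45 |
| 3% | 0.44 | 0.21 | 0.12 |

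**The case against.** The strongest reply is that the planned test is valid and answers the question as the SAP words it. SAP 6.2 compares class proportions, Protocol 9 lists NYHA among endpoints measuring proportions, and Appendix 1 labels its analysis a proportion. Chi-square tests equality of proportions and holds its 5% level. That stands: this is a choice between defensible tests, not an error.

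A reader might infer that the extra power costs nothing. It does not: a rank or trend test gives up nearly all power against non-monotone differences. Such a pattern cannot be dismissed here. Protocol 2.2 says scintigraphy can detect the disease before clinical heart failure develops, and also that diagnosis may be delayed for years. A screened ATTR-CM group could therefore mix early and advanced cases. This is why the chi-square should stay in the plan.

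A reader might also infer that the Fisher fallback will usually apply. The 79% and 44% figures hold only if ATTR-CM does not shift Class IV at all. Under the shift at issue (OR 1.3 to 1.5) the probability runs from 12% to 59%, depending on an assumed Class IV rate. Fisher's test is valid in any case.

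Nor is the Wilcoxon test for NT-proBNP in the same section an inconsistency. NT-proBNP is numerical, and the SAP assigns rank tests to non-normal numerical endpoints. And although the p-value has no direction, the planned frequency tables will show one.

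Finally, SAP 5.1 frames the study as estimation without formal hypothesis testing. That limits the consequence but does not remove the point. SAP 5.2.3 and 6.2 still prescribe tests for this endpoint, and if estimation is the aim, the absence of any effect estimate matters more.

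**Conclusion.** The point holds as an inexpensive improvement to a secondary analysis. NYHA class is compared only with order-blind tests and without an estimate of the shift. If ATTR-CM moves severity in one direction by a proportional OR of 1.3 to 1.5, the planned test gives up about 14 to 16 points of power. The loss is about 5 points at OR 1.75 and under 1 point at OR 2.

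These sizes rest on assumed class distributions, a proportional-odds shift, a two-sided 5% level and the 200 v 1800 split implied by Protocol 9. The documents do not support a stronger reading, that the chi-square is wrong or that the study's conclusions are at risk. The comparison is an unpowered baseline comparison, its type I error is correct, and the primary prevalence estimate is not touched. Parts of the documents are blacked out, so the statement that no ordinal analysis is planned applies to the readable text.

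**What to change.** In SAP 5.2.3 and 6.2, specify for NYHA class:

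- Main comparison: Wilcoxon rank sum test with tie correction, or a linear trend test with scores 1 to 4. Choose one now.
- Estimate: proportional odds ratio for a worse class, ATTR-CM v no ATTR-CM, with 95% CI. Show the three cumulative odds ratios beside it, so that a departure from proportional odds or a non-monotone pattern is visible.
- Supplementary: the frequency table and the planned chi-square or Fisher comparison.

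Leave chi-square and Fisher as the rule for unordered and yes/no variables, such as symptoms from the medical history. Align Protocol 9 if it is next amended. SAP 2 lets the SAP modify the protocol's plans and requires a protocol amendment only for major changes to the primary endpoint or its analysis.

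The cost is a sentence or two in the SAP and one extra output row, with no new data. With two tests reported, the SAP must say which is the main one before the data are seen. The main test will have little power if the true difference is non-monotone.

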6.4. Safety Summaries and Analyses

6.4.1. Adverse Events

All adverse events and serious adverse events collected at the Screening Visit, Visit 1 or during follow-up, will be coded according to the Medical Dictionary for Regulatory Activities (MedDRA) and will be summarized by system organ class and preferred terms overall and separately for HFpEF participants diagnosed with ATTR-CM and HFpEF participants not diagnosed with ATTR-CM as defined in [Section 6.1.1.1](#). Participants with non-evaluable scintigraphy grade will be summarized in a separate group. All adverse events will be listed.

6.4.2. Physical Examination

Physical examination is performed at Screening Visit only. Any abnormal findings from physical examination will be summarized using a frequency table.

7. INTERIM ANALYSES

7.1. Interim Analyses and Summaries

Interim analyses will be performed during the course of the study to allow for the reporting of data to the scientific community.

9. APPENDICES

Appendix 1. Summary of Primary, Secondary, CCI ██████████ Analyses

Endpoint	Analysis Set	ATTR-CM vs HFpEF Participants	Analysis of ATTR-CM Participants by		Analysis
			Scintigraphy Grade	NYHA Baseline Classification	
Primary					
Global prevalence of ATTR-CM among participants with HFpEF.	Evaluable	N/A	N/A	N/A	Prevalence
Sensitivity/Supplementary Analysis					
Global prevalence of ATTR-CM as defined in Section 6.1.1.1 among participants with HFpEF will be estimated using the diagnosis criteria described in the primary endpoint, but will include all participants with Scintigraphy Grade 1 diagnosed with ATTR CM in the study (regardless of the cardiac biopsy).	Evaluable	N/A	N/A	N/A	Prevalence
Prevalence of ATTR-CM as defined in Section 6.1.1.1 among participants with HFpEF (regardless of the cardiac biopsy) in sub-groups (regions, age categories, gender).	Evaluable	N/A	N/A	N/A	Prevalence
Secondary					
Prevalence of ATTR-CM as defined in Section 6.1.1.1 among participants with HFpEF in sub-groups (regions, age categories, gender).	Evaluable	N/A	N/A	N/A	Prevalence
Proportion of participants with WT and hereditary forms among participants diagnosed with ATTR-CM as defined in Section 6.1.1.1 .	All Enrolled	✓	✓	✓	Proportion

New York Heart Association (NYHA) classification.	All Enrolled	✓	✓	N/A	Proportion
NTproBNP.	All Enrolled	✓	✓	✓	Descriptive Mean

CCI

Appendix 2. List of Abbreviations

Abbreviation	Term
6-MWT	6-minute walk test
ATTR	transthyretin amyloid
ATTR-CM	transthyretin amyloid cardiomyopathy
ATTR-PN	transthyretin amyloid polyneuropathy
ECG	electrocardiogram
eGFR	estimated glomerular filtration rate
HCRU	healthcare resource utilization
HFpEF	heart failure with preserved ejection fraction
IVST	interventricular septal wall thickness
KCCQ	Kansas City Cardiomyopathy Questionnaire
KCCQ-OS	Kansas City Cardiomyopathy Questionnaire overall score
LVEF	left ventricular ejection fraction
mBMI	modified body mass index
MedDRA	Medical Dictionary for Regulatory Activities
MCR	myocardial contractile reserve
N/A	not applicable
NT-proBNP	N-terminal prohormone B-type natriuretic peptide
NYHA	New York Heart Association
SAP	statistical analysis plan
TTR	transthyretin
WT	wild-type
